3.6.1 Subject evaluable for dose decisions

Subjects in Part 1 will be evaluable for dose decisions if they satisfy one of the following criteria:

- Have had a DLT after at least one dose of MT-3724 in cycle 1; or
- In the absence of DLT, have received at least 4 of 6 (67%) doses of MT-3724 (if 6 doses are planned) or 3 of 4 doses (75%) of MT-3724 (if 4 doses are planned) and at least 14 of 21 (67%) doses of LEN.

Subjects who are not evaluable for dose decisions will be replaced.

3.6.2 DLT Criteria

A TEAE will be declared as DLT if both of the following criteria are met:

1. The TEAE occurred after the start of infusion in cycle 1 of Part 1.
 - a. If a TEAE that fulfills a DLT criterion is observed in cycle ≥ 2 of Part 1, then the sponsor may declare this event a DLT after consultation with the investigator(s).
2. The TEAE is at least possibly related to MT-3724, as determined by the sponsor after consultation with the investigator(s).

Note: TEAEs related to LEN will not be declared a DLT unless they exceed in severity the worst grade described or are not mentioned in the reference prescribing information. If a Grade ≥ 3 TEAE related to LEN is more severe than the worst grade described in the reference prescribing information or has not been reported in the reference prescribing information, then the sponsor may declare this event a DLT after consultation with the investigator(s).

The severity of TEAEs potentially fulfilling the DLT criteria will be graded according to the CTCAE v.5.0.

See [Appendix 4](#) for the type and severity of TEAEs that may qualify as DLT.

3.6.3 MTD definition

The highest MT-3724 dose that can be given in combination with LEN so that no more than 1 of 6 subjects experiences a DLT will be declared as the MTD for MT-3724 in Part 1 of this study. At least 6 subjects must be treated at the MTD dose level of MT-3724 in combination with LEN and complete cycle 1 or experience a DLT.

The MTD decision will be made by the sponsor after consultation with all investigator.

3.6.4 MTD communication plan

The investigators and medical monitor will monitor the occurrence of TEAEs that could qualify as DLT and assess the number of subjects with DLT in real time during the conduct of Part 1. If the medical monitor becomes aware that the MTD may be declared in the current dose cohort (e.g. based on the occurrence of qualifying AE/serious adverse event [SAE] in ≥ 2 subjects), then they will inform the investigators that recruitment should be suspended pending the safety review meeting. The details of cohort management and safety review during Part 1 will be described in the study manual.

3.7 Part 2 (MTD Expansion Cohort)

The purpose of Part 2 is to confirm the safety and tolerability of MT-3724 in the MTD Expansion Cohort, where MT-3724 will be given at the MTD in combination with LEN. In addition, the PK, PD, immunogenicity and tumor response at the MTD of MT-3724 in combination with LEN will be more thoroughly evaluated in Part 2.

Up to 40 subjects will be enrolled in Part 2. Subjects in Part 2 may be enrolled and treated simultaneously through competitive enrollment at multiple global study centers.

Part 2 can start only after the MTD of MT-3724 in combination with LEN is declared in Part 1; however, the screening of prospective subjects for Part 2 may begin during the review of the safety data leading to the MTD decision.

See [Section 4.3.2](#) for the principles of subject replacement in Part 2 of the study.

4 STUDY POPULATION

In addition to evaluating eligibility during the screening period, prior to first dose of MT-3724 on C1D1, the investigator must confirm there have been no changes in the subject's health that would render them medically inappropriate to begin protocol therapy.

4.1 Inclusion criteria

Subjects must meet ALL the following criteria to be eligible for the study.

1. Be adequately informed about the study and fully consent to participation as demonstrated by signing the written ICF before any screening procedure.
2. Be aged ≥ 18 years on the date of signing the informed consent form.
3. Have relapsed or refractory CD20-positive B-cell NHL that, in the investigator's opinion, could benefit from MT-3724+LEN therapy. Subjects must have proof of CD20-positive NHL, either by:
 - a. Historical biopsies (obtained with diagnosis of relapsed or refractory disease), or
 - b. Fresh biopsies.
 - c. Bone marrow biopsy, excisional lymph node biopsy, and core biopsy of any involved organ are all acceptable methods; FNA are not acceptable.
4. All subtypes of B-cell NHL may be considered for Part 1 (MT-3724 Dose Escalation). Only histologically documented DLBCL (including mixed histology) may be considered for Part 2 (MTD Expansion Cohort).
5. Have received all available approved therapies for NHL, one of which should be anti-CD20-based therapy.
 - a. Subjects whose prior therapy includes chimeric antigen receptor t-cell (CAR-T) cell therapy are eligible.
 - b. Subjects who underwent stem cell transplant (SCT) >100 days for autologous SCT or >180 days for allogeneic SCT before study drug administration and exhibited a full hematological recovery (consistent with the existing inclusion criteria requirements and without PRBC or platelet transfusions within 2 weeks of C1D1) prior to relapse are eligible.
 - c. Subjects who have been ineligible for approved therapies in the opinion of the investigator, or have refused such therapies, may be eligible at the investigator's discretion, upon sponsor approval.
6. Have bi-dimensionally measurable disease by Lugano Classification for NHL.
 - a. >1.5 cm LD_i for lymph nodes
 - b. >1.0 cm LD_i for extranodal disease
7. Have Eastern Cooperative Oncology Group (ECOG) performance status of ≤ 2 ([Appendix 6](#)).

8. Have adequate bone marrow function, as determined by all the following:
 - a. Absolute neutrophil count (ANC) $\geq 1,000/\text{mm}^3$
 - b. Platelet count $\geq 50,000 \text{ mm}^3$
 - c. Hemoglobin $\geq 8.0\text{g/dL}$
9. Have adequate kidney function, CLcr to be $\geq 50 \text{ mL/min}$ either measured or estimated using the Cockcroft-Gault formula ([Appendix 5](#)).
 - a. At the investigator's discretion, the eGFR result $<50 \text{ mL/min}$ may be verified by measurement of CLcr based on the 24-hour urine collection. Subjects with CLcr $\geq 50 \text{ mL/min}$ will be eligible irrespective of the eGFR result.
10. Have adequate hepatic function, as determined by:
 - a. Total bilirubin $<1.5 \times \text{ULN}$, or direct bilirubin $<1.5 \times \text{ULN}$ for subjects with elevated total bilirubin secondary to Gilbert's Syndrome, and
 - b. Aspartate aminotransferase $\leq 3.0 \times \text{ULN}$ (or $\leq 5 \times \text{ULN}$ if liver involvement), and
 - c. Alanine aminotransferase $\leq 3.0 \times \text{ULN}$ (or $\leq 5 \times \text{ULN}$ if liver involvement).
11. Have adequate coagulation, as determined by:
 - a. International normalized ratio or PT $\leq 1.5 \times \text{ULN}$ (unless on therapeutic anticoagulants)
 - b. Activated partial thromoplastin time $\leq 1.5 \times \text{ULN}$ (unless on therapeutic anticoagulants)
12. Albumin $\geq 3.0 \text{ g/dL}$.
13. Women of reproductive potential must have a negative pregnancy test on 2 occasions during the screening period (within 10-14 days and within 24 hours before the start of treatment). Women not of reproductive potential are female subjects who are postmenopausal (>1 year since last menstrual cycle) or permanently sterilized (e.g., hysterectomy, bilateral salpingectomy).
14. Males must agree to always use a latex or synthetic condom during any sexual contact with females of reproductive potential while taking LEN and for up to 4 weeks after discontinuing LEN, even if they have undergone a successful vasectomy. Male subjects taking LEN must not donate sperm.
15. Subjects of reproductive potential and their partners must agree to either abstain continuously from heterosexual intercourse or to use 2 methods of reliable birth control simultaneously to begin 4 weeks prior to initiating treatment with LEN until 28 days after the last dose of MT-3724 or LEN. The investigator or a designated associate should advise the subject how to achieve adequate contraception. The following birth control methods may be considered: one highly effective form of contraception – tubal ligation, IUD, hormonal (birth control pills, injections, hormonal patches, vaginal rings, or implants), or partner's vasectomy, and one additional effective contraceptive method – male latex or synthetic condom, diaphragm, or cervical cap.
16. Subjects must have life expectancy of >3 months from the start of treatment.

4.2 Exclusion criteria

Subjects who meet any of the following criteria must be excluded from the study.

Medical and surgical history

1. History or current evidence of neoplastic disease that is histologically distinct from NHL, except cervical carcinoma in situ, superficial noninvasive bladder tumors, curatively treated Stage I-II non-melanoma skin cancer. Subjects with prior, curatively treated cancer >2 years ago before the start of treatment can be enrolled.
2. Current evidence of new or growing brain or spinal metastases during screening. Subjects with known brain or spinal metastases may be eligible if they:
 - a. Had radiotherapy or another appropriate therapy for the brain or spinal metastases; concurrent prophylactic treatment is allowed
 - b. Neurologic symptoms must be stable and no worse than Grade 2
 - c. Have evidence of stable brain or spinal disease on CT or MRI scan obtained within 4 weeks of signing the ICF and compared with prior imaging results
 - d. Do not require chronic steroid therapy (or, if applicable, have been stable on steroid dose of no more than prednisone 20mg/day or equivalent by C1D1)
3. Current evidence of Graft versus Host Disease.
4. Current evidence of CTCAE Grade >1 toxicity (due to prior cancer therapy) before the start of treatment, except for hair loss and those Grade 2 toxicities listed as permitted in other eligibility criteria.
5. Current evidence of incomplete recovery from surgery or radiotherapy before the start of treatment, or planned surgery or radiotherapy at any time until the EoT Visit, except minor elective interventions deemed acceptable by the investigator.
6. Current evidence of significant (CTCAE Grade ≥ 2) infection or wound within 4 weeks before the start of treatment.
 - a. Subjects with Grade 2 infection that has stabilized or improved with oral anti-infectives before the start of treatment may be eligible at the sponsor's discretion.
7. Current evidence of significant cardiovascular disease including, but not limited to the following conditions:
 - a. Unstable angina (symptoms of angina at rest) or new-onset angina within 3 months before the start of treatment.
 - b. Arterial thrombosis or pulmonary embolism within 3 months before the start of treatment.
 - c. Myocardial infarction or stroke within 3 months before the start of treatment.
 - d. Any of the following within 3 months before the start of treatment with MT-3724: pericarditis (any CTCAE grade), pericardial effusion (CTCAE Grade ≥ 2), non-malignant pleural effusion (CTCAE Grade ≥ 2) or malignant pleural effusion (CTCAE Grade ≥ 3).
 - e. Congestive heart failure (NYHA Class III or IV; [Appendix 7](#)) at Screening or LVEF <45%, assessed by Echo or multiple-gated acquisition (MUGA) scan within 1 month before starting study treatment (inclusion of subjects with LVEF between 40%-45%

should be discussed and approved by the sponsor). Echo or MUGA scan performed within 6 months before screening and at least 28 days after the last cancer therapy is acceptable provided the subject has not received any potential cardiotoxic agents since then.

- f. Cardiac arrhythmia requiring anti-arrhythmic therapy at screening. Subjects receiving digoxin, calcium channel blockers, or beta-adrenergic blockers are eligible at the investigator's discretion after consultation with medical monitor if the dose has been stable for ≥ 2 weeks before the start of treatment with MT-3724. Subjects with sinus arrhythmia and infrequent premature ventricular contractions are eligible at the investigator's discretion.
8. QTcF >480 ms, determined as the average from three QTcF values on the triplicate ECG obtained at screening.
9. Current evidence of uncontrolled human immunodeficiency virus (HIV), hepatitis B virus (HBV) or hepatitis C virus (HCV) at screening. Serology testing is not required if seronegativity is documented in the medical history, and if there are no clinical signs suggestive of HIV or hepatitis infections, or suspected exposure. The following exceptions apply for subjects with positive viral serology:
 - a. Subjects with HIV and an undetectable viral load and CD4+ T-cells counts ≥ 350 cells/microliter may be enrolled, but must be taking appropriate opportunistic infection prophylaxis, if clinically relevant.
 - b. Subjects with positive HBV serology are eligible if they have an undetectable viral load and the subject will be receive antiviral prophylaxis for potential HBV reactivation per institutional guidelines.
 - c. Subjects with positive HCV serology are eligible if quantitative PCR for plasma HCV RNA is below the limit of detection. Concurrent antiviral HCV treatment and have an undetectable viral load.
10. Women who are pregnant or breastfeeding.
11. History or current evidence of hypersensitivity to any of the study drugs, or of current hypersensitivity requiring systemic steroids at doses >20 mg/day prednisone equivalent
12. History or current evidence of any other medical or psychiatric condition or addictive disorder, or laboratory abnormality that, in the opinion of the investigator, may increase the risks associated with study participation, or require treatments that may interfere with the conduct of the study or the interpretation of study results.

Prior treatments

13. Prior treatment with MT-3724.
14. Received anti-CD20 mAb therapy within the following periods before the start of treatment:
 - a. Rituximab (Rituxan®): 84 days; if a subject had received RTX within 37 weeks before the start of treatment, then a serum RTX level must be negative (<500 ng/mL) at screening.
 - b. Obinutuzumab (Gazyva®): 184 days
 - c. Ofatumumab (Arzerra®): 88 days

15. Received therapy for NHL (except the anti-CD20 mAb therapies and radioimmunoconjugates) within 4 weeks before the start of treatment.
Radioimmunoconjugates are excluded within 12 weeks before the start of treatment. For small molecules (MW <0.9kDa), the washout shall be 2 weeks or 5 half-lives, whichever is longer ([Macielag 2012](#)).
16. Any investigational drug treatment from 4 weeks or 5 half-lives of the agent before the start of treatment, whichever is longer, until the EoT Visit.
17. Received radiotherapy to tumor lesions that would be chosen as target lesions (measurable disease) within 4 weeks before the start of treatment, unless the lesion exhibited objective progression between the radiotherapy and screening according to the Lugano Classification for NHL.
 - a. Palliative radiotherapy to non-target lesions may be permitted at the investigator's discretion after consultation with the medical monitor. See [Section 5.10](#) for more information on the use of radiotherapy.
18. Received any live vaccines within 4 weeks before the start of treatment, unless the investigator believes benefits outweigh risk, after approval with medical monitor.
19. Require the use of systemic immune modulators during study treatment
 - a. Systemic immune modulators include, but are not limited to, systemic corticosteroids at doses >20 mg/day or prednisone equivalent, cyclosporine and tacrolimus. Please see [Section 5.9](#) for more details and exceptions.

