6.1.6 Prior radiotherapy

Prior radiotherapy for NHL administered at any time before the start of treatment will be assessed and documented at screening.

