6.6 Efficacy assessments: Radiological Assessment of Tumor Response

The tumor response assessment should be performed at the following time points:

- At Screening:
 - The investigator is encouraged to obtain the screening tumor scan as close as possible to the start of treatment within 28 days of C1D1.
- Within 7 days before the start of treatment on C3D1 and every other cycle thereafter (i.e. Between D23 and D28 of the cycle). The original schedule needs to be maintained even if there is a delay in dosing.
- Within 7 days of the EoT Visit (**only** if the previous tumor scan has been performed >4 weeks before the EoT Visit)

The investigator and the radiologist should carefully consider if the increase from baseline in tumor size could be “pseudoprogression” due to the tumor flare induced by the study drug(s).

Unscheduled tumor response assessment by FDG-PET-CT (or CT/MRI, where applicable) may be ordered at the investigator’s discretion.

Efficacy of the study drugs (tumor response) will be assessed by the scan of all anatomic regions involved with the measurable disease. Positron emission tomography-computed tomography should be used in subjects with FDG-avid tumor histology. Computed tomography or MRI should be used in subjects with tumor histology of low or variable FDG avidity. Diagnostic quality CT should be collected for all subjects at baseline, whenever possible.

Tumor response in subjects with FDG-avid tumor histology will be determined using the 5-point scale (5PS) according to the Lugano Classification for Lymphoma ([Cheson 2014](#)) adjusted according to LYRIC (lymphoma response to immunomodulatory therapy criteria) ([Cheson 2016](#)). An overview of NHL response criteria for FDG avid and non-avid NHL is presented in [Appendix 3](#).

The same technique (e.g. slice thickness, field of view) should be used for all scans during the study treatment period. Preferably, all scans should be interpreted by the same investigator during the study whenever possible. Scans must meet the SOC for imaging of lesions in the respective organ system(s).

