Response and Site	PET-CT-Based Response	CT/MRI-Based Response
Complete	Complete metabolic response	Complete radiologic response (all of the following)
Lymph nodes and extralymphatic sites	5PS score of 1, 2, or 3 ¹ with or without residual mass. It is recognized that in Waldeyer's ring or extranodal sites with high physiologic uptake or with activation within spleen or marrow (e.g., with chemotherapy or myeloid colony-stimulating factors), uptake may be greater than normal mediastinum and/or liver. In this circumstance, complete metabolic response may be inferred if uptake at sites of initial involvement is no greater than surrounding normal tissue even if the tissue has high physiologic uptake	Target nodes/nodal masses must regress to ≤ 1.5 cm in LD _i No extralymphatic sites of disease
Nonmeasured lesion	Not applicable	Absent
Organ enlargement	Not applicable	Regress to normal
New lesion(s)	None	None
Bone Marrow	No evidence of FDG-avid disease in marrow	Normal by morphology; if indeterminate, IHC negative
Partial	Partial metabolic response	Partial remission (all of the following)
Lymph nodes and extralymphatic sites	Score 4 or 5 on the 5PS (Table 13) with reduced uptake compared with baseline and residual mass(es) of any size. At interim, these findings suggest responding disease. At end of treatment, these findings indicate residual disease	$\geq 50\%$ decrease in SPD of up to 6 target measurable nodes and extranodal sites When a lesion is too small to measure on CT, assign 5 mm x 5 mm as the default value When no longer visible, 0 x 0 mm For a node >5 mm x 5 mm, but smaller than normal, use actual measurement for calculation
Nonmeasured lesion	Not applicable	Absent/normal, regressed, but no increase
Organ enlargement	Not applicable	Spleen must have regressed by $>50\%$ in length beyond normal
New lesion(s)	None	None

Bone Marrow	Residual uptake higher than uptake in normal marrow but reduced compared with baseline (diffuse uptake compatible with reactive changes from chemotherapy allowed). If there are persistent focal changes in the marrow in the context of a nodal response, consideration should be given to further evaluation with MRI or biopsy or an interval scan	Not applicable
No response or stable disease	No metabolic response	Stable disease

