¹A score of 3 in many subjects indicates a good prognosis with standard treatment, especially if at the time of an interim scan. However, in trials involving PET where de-escalation is investigated, it may be preferable to consider a score of 3 as inadequate response (to avoid undertreatment). Measured dominant lesions: Up to six of the largest dominant nodes, nodal masses, and extranodal lesions selected to be clearly measurable in two diameters. Nodes should preferably be from disparate regions of the body and should include, where applicable, mediastinal and retroperitoneal areas. Non-nodal lesions include those in solid organs (e.g., liver, spleen, kidneys, lungs), gastrointestinal involvement, cutaneous lesions, or those noted on palpation. Nonmeasured lesions: Any disease not selected as measured, dominant disease and truly assessable disease should be considered not measured. These sites include any nodes, nodal masses, and extranodal sites not selected as dominant or measurable or that do not meet the requirements for measurability but are still considered abnormal, as well as truly assessable disease, which is any site of suspected disease that would be difficult to follow quantitatively with measurement, including pleural effusions, ascites, bone lesions, leptomeningeal disease, abdominal masses, and other lesions that cannot be confirmed and followed by imaging. In Waldeyer's ring or in extranodal sites (e.g., gastrointestinal tract, liver, bone marrow), FDG uptake may be greater than in the mediastinum with complete metabolic response, but should be no higher than surrounding normal physiologic uptake (e.g., with marrow activation as a result of chemotherapy or myeloid growth factors).

²See original paper ([Cheson 2014](#), [Cheson 2016](#)) for more detailed information on immune related response.

Lugano 5PS range ([Cheson 2014](#))

The 5PS ranges from a score of 1 (where no uptake is discernible in the lesion) to a score of 5 (where the uptake in the lesion is markedly increased compared to the uptake in the liver parenchyma). A single 5PS score, which represents the most FDG-avid (i.e., metabolically intense) area of disease (across all index and non-index lesions), is assigned for each PET/CT scan in the study, see Table 13.

Table 13: Modified Lugano 5-point scale (5PS)

Score	Description
1	No uptake
2	Uptake \leq mediastinum
3	Uptake $>$ mediastinum but \leq liver
4	Uptake moderately increased above liver at any site

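### Exclusion 17 asks for progression after radiotherapy only within 4 weeks of treatment, so residual shrinkage of a lesion irradiated earlier can be scored as response to MT-3724 plus lenalidomide

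*Protocol*

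**What the plan says.** Exclusion 17 (Protocol 4.2, repeated in the synopsis) applies to a subject who "Received radiotherapy to tumor lesions that would be chosen as target lesions (measurable disease) within 4 weeks before the start of treatment". The same criterion then gives one way out, under which the bar holds "unless the lesion exhibited objective progression between the radiotherapy and screening according to the Lugano Classification for NHL". The progression test is thus an exception to the 4-week bar and has no role once 4 weeks have passed.

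The other relevant provisions are:

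- **Eligibility.** Inclusion 6 (Protocol 4.1) requires the subject to "Have bi-dimensionally measurable disease by Lugano Classification for NHL" and adds size limits only. It does not ask for an unirradiated lesion.
- **Target selection.** The notes to Table 12 in Appendix 3 describe the measured lesions as "Up to six of the largest dominant nodes, nodal masses, and extranodal lesions selected to be clearly measurable in two diameters". Irradiation is not mentioned.
- **Scan timing.** Protocol 6.6 says of baseline: "The investigator is encouraged to obtain the screening tumor scan as close as possible to the start of treatment within 28 days of C1D1". The first response scan is due "Within 7 days before the start of treatment on C3D1 and every other cycle thereafter".
- **Scoring.** On CT/MRI a partial remission needs a 50% or greater "decrease in SPD of up to 6 target measurable nodes and extranodal sites". On PET-CT a partial metabolic response needs uptake below baseline, with no minimum percentage stated.
- **Data collected.** Protocol 6.1.6: "Prior radiotherapy for NHL administered at any time before the start of treatment will be assessed and documented at screening". Nothing links this record to lesion selection or to an analysis.

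**The concern.** By waiving the 4-week bar only after progression, the protocol treats a recently irradiated lesion as a trustworthy target only once it has grown again. That test lapses on Day -29, one day before the 28-day window for the baseline scan opens. A lesion that is still regressing can then serve as the baseline against which the study drugs are judged.

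There is no control arm, and response is the local investigator's reading. Continued shrinkage from radiotherapy would look the same as a drug effect, and following the plan exactly would credit it to the drugs in ORR and BORR.

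**Working it through.** **1. Does another provision close the gap?**

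- Protocol 5.9 prohibits radiotherapy to would-be target lesions during the study, not before it.
- Exclusion 5 concerns incomplete recovery from radiotherapy, not residual regression or the choice of targets.
- Protocol 6.6 and Appendix 3 do not mention irradiated lesions.
- Protocol 6.6.1 allows a blinded central review if the sponsor wants one, but gives it no rule on irradiated lesions.
- Protocol 7.9 and the response subsections under SAP 7.2 contain no flag, exclusion or sensitivity analysis.

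The gap stays open.

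**2. Timing.** Take the last radiotherapy 29 days before C1D1. Cycle 2 Days 23 to 28 fall 28 + 22 = 50 to 28 + 27 = 55 days after C1D1.

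- Radiotherapy to first response scan: 29 + 50 = 79 to 29 + 55 = 84 days (11.3 to 12 weeks).
- Earliest baseline, 28 days before C1D1: 29 - 28 = 1 day after radiotherapy. Baseline to first response scan is 28 + 50 = 78 to 28 + 55 = 83 days.
- Late baseline, 1 day before C1D1: 29 - 1 = 28 days after radiotherapy. Baseline to first response scan is 1 + 50 = 51 to 1 + 55 = 56 days.

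A late baseline shortens the exposed interval but leaves at least 51 days.

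**3. When can one irradiated lesion decide a CT partial remission?** Let f be its share of baseline SPD, s its fractional shrinkage and o the shrinkage of all other targets. The 50% threshold is met when f·s + (1 - f)·o ≥ 0.5, so f ≥ (0.5 - o)/(s - o).

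| Shrinkage of irradiated lesion (s) | Share needed, others unchanged (o = 0) | Share needed, others shrink 30% (o = 0.3) |
|---|---|---|
| 60% | 0.5/0.6 = 83% | 0.2/0.3 = 67% |
| 80% | 0.5/0.8 = 63% | 0.2/0.5 = 40% |
| 100% | 0.5/1.0 = 50% | 0.2/0.7 = 29% |

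The lesion must dominate the measured disease, or add to a partial effect elsewhere. The shrinkage values are illustrative; the documents give none.

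**4. Size.** The plan states no target ORR or power to reproduce. With 40 Part 2 subjects (Protocol 3.7), one response is 1/40 = 2.5 points. For illustration, assume 13 true responders, close to the 33% ORR that Protocol 1.3.1 cites for rituximab plus lenalidomide. Intervals are exact (Clopper-Pearson).

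| Misattributed responses (assumed) | Observed | ORR | Exact 95% CI |
|---|---|---|---|
| 0 | 13/40 | 32.5% | 18.6 to 49.1 |
| 1 | 14/40 | 35.0% | 20.6 to 51.7 |
| 2 | 15/40 | 37.5% | 22.7 to 54.2 |
| 4 | 17/40 | 42.5% | 27.0 to 59.1 |

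**The case against.** The strongest reply is that the harmful case is narrow. The 1-day gap needs radiotherapy on Day -29 and a scan on the first permitted day, whereas the protocol asks for the scan close to treatment. Shrinkage before the baseline scan does not count. The population is relapsed or refractory, and Protocol 1.5 describes the disease as advanced and progressive, so most subjects should have active disease elsewhere. SPD is summed over up to six lesions, and the 5PS score comes from the most avid area, so active unirradiated disease dilutes or blocks a false response. All of this stands and limits the concern to subjects whose irradiated lesion is the only or dominant one. Inclusion 6 allows such subjects, and the request for a scan close to treatment is encouragement rather than a rule.

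It is also fair that 4 weeks matches the general washout for NHL therapy in exclusion 15. The difficulty is not the length of the interval but that the progression test disappears after it.

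Four stronger readings are tempting, and the documents support none of them:

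- **That ORR will be inflated by a stated amount.** The documents give neither the frequency of such lesions nor how often they keep regressing. Some of these subjects would also respond to the drugs anyway, so not every one is a false responder.
- **That DOR is biased upward.** A radiotherapy-driven responder could equally progress early at another site and shorten DOR.
- **That the 12-week washout for radioimmunoconjugates shows the protocol recognises longer radiation effects.** No reason is given for the 12 weeks.
- **That moving past the rituximab-lenalidomide rate changes a conclusion.** That rate is background, not a success threshold. No test is planned, and the intervals for 13/40 and 15/40 both contain 33%.

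**Conclusion.** The point holds as a possibility built into the rules: residual radiotherapy regression can be scored as PR or CR. It does not show that this will happen in any given number of subjects.

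The size is 2.5 points of Part 2 ORR per misattributed response, assuming 40 subjects in the denominator. The number of such responses is unknown, and the counts of 1, 2 and 4 above are assumptions. Response is a secondary, descriptive endpoint, so the primary safety and MTD objective is not affected. The change is still worth making, because it extends a test the protocol already uses, removes a bias that the single-arm design cannot detect, and costs little.

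**What to change.** Amend exclusion 17 and inclusion 6 (with the synopsis) and Appendix 3 as follows:

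- A lesion irradiated at any time before C1D1 qualifies as measurable disease, or as a target lesion, only if it objectively progressed after that radiotherapy.
- Other irradiated lesions are followed as non-target. Their shrinkage or fall in uptake cannot establish a PR. They still count for the 5PS score, for ruling out CR, and for PD. Dropping them from response assessment altogether would be wrong, because a persistently avid irradiated lesion would then no longer block a CR.

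For subjects already enrolled, first confirm that the CRF records the site and date of prior radiotherapy, since Protocol 6.1.6 does not specify either. Then add to the SAP one sensitivity analysis of ORR and BORR, keeping the safety-population denominator. It would count any response that rests on an irradiated, non-progressed target lesion as a non-response.

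The cost is some protocol wording, one CRF check and one extra table row. A few subjects whose only measurable lesion is irradiated and has not progressed would become ineligible. If site and date were not captured, they would have to be retrieved from source records before the sensitivity analysis could be run.
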